6. STUDY POPULATION

6.1. Participant Disposition

For Main Study analyses, all references to participant disposition, etc., refer only to the Main Study and exclude the OLE.

The number of participants who signed informed consent, or signed consent but were not randomized along with reason for screening failure will be summarized overall and by region and for select countries.

The number of participants included in each analysis population will be presented by treatment group. The participants who are excluded from each of the analysis population and the reason for exclusion (for example, exclusion from mITT population because they were not treated, or if they were treated but have no post-baseline in-clinic UHDRS-TFC assessment), will be summarized by treatment group. These participants will be identified in the listing of participants with populations in which they are included.

The end of the Main Study is reached when all participants who have signed informed consent, been randomized and treated have either completed through Week 65 or discontinued from the study (defined in Section 5.5.5). At the end of Main Study, the number of participants who completed the Main Study portion as well as those that withdraw from the treatment or study will be summarized along with the reason for withdrawal. The denominator for calculating the percentages will be the number of participants within the treatment group in the population being summarized.

In the OLE analyses, the numbers of participants who have enrolled in the OLE portion, who are included in each analysis population, who have completed the OLE, and who withdraw from the treatment or study along with the reasons will be summarized.

6.2. Demographics and Baseline Characteristics

Participant demographics and baseline characteristics will be examined to assess the comparability of the treatment groups. The continuous variables of participant age, weight, height, body mass index, efficacy and safety scales scores at Baseline will be summarized using descriptive statistics.

The categorical variables of participant sex, race, ethnicity, HD stage (HD1 or HD2) and use of neuroleptics will be summarized using count and percentages for each category.

Other baseline and disease characteristics may also be summarized.

A category will indicate participants with missing data.

Cytosine-adenosine-guanine (CAG) repeat length was reported by participants at Screening and recorded in the EDC. For participants who did not report CAG repeats, a plasma sample was taken and sent to a laboratory to determine the CAG repeat length. For participants whose CAG repeats were reported by both participant and laboratory, the value of CAG repeats as determined by the laboratory test will be used.

6.3. Participant Inclusion and Exclusion Criteria

Reasons for screen failure including inclusion and exclusion criteria not met prior to randomization will be listed for each participant.

6.4. Medical History

All medical history will be coded as per Section 5.3. Participants with a medical history assessment, by system organ class (SOC) and PT will be summarized. Participants are counted only once in each SOC and only once in each PT category. SOC and PT within SOC will be ordered by descending incidence of all participants.

6.5. Prior and Concomitant Medications / Therapies

All medications (both prior and concomitant) will be coded as per Section 5.3.

Prior medications will include all medications which had a start date prior to the first day of study drug treatment regardless of when it ended. This includes medications taken and stopped prior to V2 Baseline Visit (day of first study drug treatment) or started prior to V2 and continued to be taken on or after V2. Any medication given at least once after V2 will be defined as a concomitant medication.

Concomitant medications are defined as medications continued or newly received by the participants during Main Study Treatment Period or OLE Treatment Period (see definition in Section 5.5.7). If a participant took a medication during a specific Treatment Period, this medication will be attributed to the treatment the subject received during this Treatment Period. As a result, one medication could be attributed to both Main Study and OLE Treatment Periods for a participant. If missing or partial dates indicate a medication may have been taken after first day of study drug treatment, it will be considered a concomitant medication.

The incidence of prior and concomitant medication use will be separately summarized using descriptive statistics by WHO (ATC) anatomical therapeutic class and PT (Standardized Name) for each treatment group and overall in the safety population. Participants are counted only once in each therapeutic class category, and only once in each PT category.

Non-pharmacological therapies and procedures will be classified by MedDRA SOC and PT, and will be reported by treatment group and overall for the safety population.

A separate summary of prior and concomitant medications taken for COVID-19 symptoms, use of tetrabenazine and deutetrabenazine or antidepressants, may be presented separately by treatment groups.

6.6. Protocol Deviations

All-important deviations related to study inclusion or exclusion criteria, conduct of the trial, participant management or participant assessment will be summarized by site and grouped into different categories, such as:

- those who entered the study even though they did not satisfy the entry criteria
- those who developed withdrawal criteria during the study but were not withdrawn

- those who received the wrong treatment or incorrect dose
- those who received an excluded concomitant treatment

Additional details of reviewing and classifying PDs as important are detailed in the Protocol Deviation Management Plan.

In the CSR Appendix 16.2.2, individual participants with important PDs will be listed.

Final categorization of PDs will be done prior to database lock and unblinding.

Since this trial is being conducted during the COVID-19 pandemic, separate summaries of PDs related to COVID-19 were planned to be tabulated by treatment groups. However since there were no important PDs due to COVID-19 no separate Table was created. Additional analyses may also be conducted to see the impact of these deviations on interpretation of key safety or efficacy analyses. Since the impact of COVID-19 related events such as AEs, medications taken, etc., will not be fully known until the trial has progressed sufficiently, these will be finalized prior to locking the database and unblinding the study.

7. EFFICACY ANALYSIS

7.1. General

Study procedures and timing are summarized in the SoA ([Table 1](#) - Main Study and [Table 2](#) – OLE).

Efficacy analyses will be conducted using the estimand framework described in the ICH E9 R(1) Guidance and related publications². The estimands will be described in detail in the endpoint analysis sections hereafter.

7.1.1. Intercurrent Events (ICEs) and Estimand Strategy

The ICEs considered for the PROOF-HD trial include treatment discontinuation due to, for example, death, AEs, progressive disease, or meeting Stopping Rules for QT/CrCl/psychiatric reasons.

If a participant has COVID-19 symptoms, their visit can be delayed within a reasonable period (up to 4 weeks) to perform UHDRS-TFC and other efficacy and safety assessments until after their COVID-19 symptoms have resolved. There is also a low likelihood of participants stopping study drug or discontinuing from study due to COVID-19. If intermittent efficacy assessments are missing due to COVID-19 impact, it will be handled by analysis, such as MMRM, under MAR assumptions³.

Also, since pridopidine is taken over a long term (65 to 78 weeks) in the Main Study, temporary treatment interruptions are expected to have minimal impact on key efficacy endpoints.

ICH E9 R(1) describes five strategies to address ICEs (Mallinckrodt et. al., 2020; Ratitch et. al., 2020a and 2020b) which include:

- (1) **Treatment Policy** (similar to ITT principle) where the ICE is ignored;
- (2) **Composite** where the ICE is taken to be a component of the endpoint as in a responder analysis where participants who die due to disease progression are considered non-responders;
- (3) **Hypothetical** where hypothetical scenarios are considered in which the ICE did not occur such as excluding observations where the UHDRS was measured while the participant was exhibiting COVID-19 symptoms;
- (4) **Principal Stratum**, where the effect of the treatment is considered only in the stratum of interest such as excluding participants infected by COVID-19 anytime during the trial, and excluding participants on antipsychotics;
- (5) **While on Treatment**, where the response to the treatment prior to discontinuing treatment is of interest.

For the PROOF-HD trial we will use the treatment policy, composite, hypothetical strategies, and/or a combination of strategies to address the specific impact of ICEs on efficacy.

Based on the regulatory feedback, the main estimand for the primary endpoint, change from Baseline in UHDRS-TFC at Week 65, will be defined separately for the EMA and non-EMA regions.

- For the EMA region, an estimand using a composite of treatment policy and hypothetical strategies is defined for the primary analysis. The treatment policy strategy will apply to all observed values including those collected after treatment discontinuation, and the hypothetical strategy will apply to missing values using ~~PMM~~ with control-based pattern imputation under MNAR assumptions (as described in Section 5.8.1.2).
- For the non-EMA regions, the primary analysis will be based on an estimand using treatment policy strategy, under which all observed data will be used regardless of occurrence of ICEs.

For the EMA region, the estimand applying treatment policy strategy (i.e., the primary estimand for the non-EMA regions) will be used as a supportive estimand, while for the non-EMA regions, the estimand applying a composite of treatment policy and hypothetical strategies (i.e., the primary estimand for EMA region) will be used as a supportive estimand.

The main estimands for secondary and exploratory endpoints will be the same for both EMA and non-EMA regions. The main estimand for key secondary endpoint, change from Baseline in cUHDRS at Week 65, will be based on treatment policy strategy and mITT population. The binary secondary endpoints, for example, the proportion of participants with improvement or no worsening in UHDRS-TFC, will use combined composite and hypothetical strategies for the main estimand. In this estimand, participants who discontinue the treatment due to disease progression-related death, or meet the Stopping Rules will be considered non-responders, while the participants who discontinue the treatment for other reasons will be imputed by hypothetical values from treatment discontinuation onward as if the participants had continued receiving the study treatment (MAR assumptions). A similar combined composite and hypothetical strategy estimand may be used for sensitivity analyses with MNAR MI under hypothetical strategy.

Other secondary and exploratory efficacy endpoints for both EMA and non-EMA regions, evaluated as changes from Baseline, will follow treatment policy strategy based estimand. Binary endpoints indicated for responder analyses will follow a similar estimand strategy as described above, where appropriate.

7.1.2. Analysis Populations

The ITT population is the main analysis population of primary endpoint for EMA region. The mITT population is the main analysis population for primary endpoint in non-EMA regions.

For all other efficacy analyses, the mITT population is the main analysis population in both EMA and non-EMA regions. The ITT and PP populations will also be used as sensitivity analyses to show robustness of results for select secondary endpoints.

7.2. Primary Efficacy Variable and Analysis

The primary efficacy variable for this study is the change from Baseline to Week 65 in the UHDRS-TFC. The calculation of the UHDRS-TFC is detailed in Appendix 12.1.1.

The null hypothesis represents no difference between the therapeutic efficacy response in the active treatment group compared to the placebo group:

$$H_0: \mu_A = \mu_P$$

$$H_A: \mu_A \neq \mu_P$$

Where μ_A is the mean change from Baseline to Week 65 in UHDRS-TFC for participants randomized to pridopidine (Active) and μ_P is the mean change from Baseline to Week 65 in UHDRS-TFC for participants randomized to the placebo group. Under the alternative hypothesis, there exists a difference between the therapeutic efficacy response in the pridopidine (active) group compared to the placebo group.

Based on regulatory feedback, the hypothesis testing will be based on the main estimand separately defined for EMA and non-EMA regions.

For non-EMA regions, the main estimand is defined as **non-EMA-Estimand**:

- Treatment: Pridopidine 45 mg bid or placebo (on background of standard of care) that participants are randomized to
- Population: Early HD Participants (HDI & HD2) defined through the study inclusion/exclusion criteria. The mITT population will be used in analyzing this estimand
- Variable: Change from Baseline to Week 65 in UHDRS-TFC
- Population Level Summary: LS-Mean difference between pridopidine and placebo from MMRM model in change of UHDRS-TFC from Baseline to Week 65
- ICEs and Strategies for Addressing ICEs:

Treatment policy strategy will be used to handle the ICEs, where occurrence of an ICE is irrelevant. All observed values will be used regardless of occurrence of an ICE. No imputation is performed.

Analysis will be performed on in-clinic observed data using MMRM. The model will include the following effects:-treatment, Baseline UHDRS-TFC, region (Europe, North America), neuroleptic use (yes, no), Baseline HD stage (HDI and HD2), categorical week, and treatment by categorical week interaction.

The unstructured covariance matrix for repeated observations within participants will be used. If the model does not converge, then a simpler covariance structure with fewer parameters will be used, and we will examine these structures in the following order based on the first structure below that converges:

1. Toeplitz with heterogeneity (TOEPH),
2. Autoregressive with heterogeneous (1) [ARH(1)],
3. Compound symmetry with heterogeneous variances (CSH),
4. Toeplitz (TOEP),
5. Autoregressive (1) [AR(1)], and
6. Compound Symmetry (CS).

Denominator degrees of freedom for the F-test for fixed effects will be estimated using the Kenward-Roger approximation. The least square mean (LSM) and standard error (SE) of the LSM for each treatment group, the 95% CI and p-value for the comparisons (change from Baseline in pridopidine 45 mg bid vs. placebo) will be presented at Week 65.

For EMA regions, the main estimand is defined as **EMA-Estimand**:

- Treatment: Pridopidine 45 mg bid or placebo (on background of standard of care) that participants are randomized to
- Population: Early HD Participants (HDI & HD2) defined through the study inclusion/exclusion criteria. The ITT population will be used in analyzing this estimand
- Variable: Change from Baseline to Week 65 in UHDRS-TFC
- Population Level Summary: LS-Mean difference between pridopidine 45 mg bid and placebo from MMRM model in change of UHDRS-TFC from Baseline to Week 65
- ICEs and Strategies for Addressing ICEs:

ICEs include treatment discontinuation or death and will be handled by a composite of treatment policy and hypothetical strategies.

- Treatment policy strategy will apply to all observed values including those collected after treatment discontinuation as these values reflect the remaining off-drug treatment effect in reality.
- Hypothetical strategy will apply to missing values after the last observed values. The method of MI will be applied to impute the missing data using PMM with control-based pattern imputation under MNAR assumptions (details in Section 5.8.1).

Since UHDRS-TFC is used as a continuous variable in the MI procedure, the imputed values will take continuous values instead of the discrete values ranging from 0 to 13. To avoid the influence of extreme values outside the range, the continuous values will be categorized to 0 if the imputed values < 0.5 , and to 13 if the imputed values ≥ 12.5 . All the other values in $[0.5, 12.5)$ will be rounded to the nearest integer between 1 and 12.

The MI method uses SAS PROC MI and MIANALYZE to generate multiple complete datasets and combine the model results from them as described in Section 5.8.1. The LSM and associated SE for each treatment group, the 95% CI and p-value for the comparisons (pridopidine 45 mg bid vs. placebo) will be presented at Week 65.

In addition, actual observed values and changes from Baseline to each visit in the UHDRS-TFC will be summarized using descriptive statistics.

For all analysis at Week 65 only data through the Week 65 visit will be included.

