3.3. Sample Size and Power Considerations

Based on experience with early HD participants in the prior Phase 2 PRIDE-HD study, we expect the difference in mean change from Baseline to Week 65 between the 45 mg bid treated and placebo groups to be 0.7 points on the UHDRS-TFC with a standard deviation (SD) of 1.9 points.

A total sample size of 372 participants will provide 94% power to detect a between-group difference of 0.7 points in the mean change from Baseline to 65 weeks in the UHDRS-TFC score, with an SD of 1.9 points, using a two-tailed t-test at a significance level of 0.05. Assuming a drop-out rate of 22.5%, a total of 480 participants will be randomized. The sample size was calculated using SAS version 9.4 PROC POWER.

Based on feedback from Regulatory Authorities, the power assessment was updated as below. Assuming a dropout rate of 22.5 % in each treatment group early in the study, under assumption of Missing Not at Random (MNAR) with imputed values for all discontinued participants estimated based on the trajectory of placebo participants with available data, we anticipate a difference in change from Baseline to imputed values at Week 65 for this group to be 0.1 points. The overall difference would then be 0.565 (0.7*0.775+0.1*0.225) or 0.7 points for the 77.5% completers and 0.1 points for the 22.5 % participants who discontinue and have imputed data at Week 65. A difference of 0.565 points with SD of 1.9 with a sample size of 480 participants would provide 90% power (SAS V 9.4 PROC POWER).

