7.3.3. Other Efficacy Analysis

To explore potential impact of other confounding factors on efficacy, the primary efficacy endpoint, select secondary and exploratory endpoints analyses may be conducted if there are enough participants in these cohorts.

Following sensitivity analyses may be performed, where applicable:

- Similar to non-EMA-Estimand with population changed to Week 65 PP Population
- Non-EMA Estimand with an additional covariate, CAP score, included in the analysis model
- EMA-Estimand with an additional covariate, CAP score, included in the analysis model
- A sensitivity analysis excluding those who had received any neuroleptics during the study that could impact efficacy may be performed.
- In addition, further sensitivity analysis may be conducted excluding those who had changes in neuroleptic use after randomization.

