7.6. Other Exploratory Efficacy Variable and Analyses

Other exploratory efficacy variables include:

- Change from Baseline to Weeks 26, 52, 65 and 78 in PBA-s domains subscale scores and total scores
- Change from Baseline to Weeks 26, 52, 65 and 78 in HDQoL

These will be analyzed similar as described in Section 7.5 for non-multiplicity adjusted secondary efficacy variables in their main estimand.

Responder analyses for select efficacy endpoints, such as UHDRS-TFC and cUHDRS, using clinically meaningful thresholds may be performed.

In addition, the observed virtual UHDRS-TFC assessments at virtual Baseline, Weeks 13, 32, and 58 and change from virtual Baseline (Day -7 Visit) at each post-baseline virtual visit will be summarized.

The impact of PIN_{HD}, defined as prognostic index normed for HD, on treatment effects for select efficacy variables may be explored using categorized PIN_{HD} score, where PIN_{HD} = (PI_{HD} - 883) / 1044, and PI_{HD} = 51 × TMS + (-34) × SDMT + 7 × Age × (CAG - 34), defined as prognostic index for HD (10).

Treatment effect on change from Baseline in weight over visits may also be explored adjusting for sex and age.

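### The primary MMRM is valid, but it may give up modest precision by omitting CAP score and a Baseline TFC-by-week term

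*SAP*

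**What the plan says.** **Primary model.** SAP 7.2 gives the fixed effects as treatment, Baseline UHDRS-TFC, region, neuroleptic use, "Baseline HD stage (HDI and HD2), categorical week, and treatment by categorical week interaction". Protocol 9.4.2 names the same set for Weeks 26, 39, 52 and 65. Neither contains CAP score or an interaction of Baseline TFC with week, and neither gives a reason.

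**CAP elsewhere in the SAP.** Section 7.3.2 defines CAP as age × (CAG − 33.66) and uses its median for subgroups. Section 7.3.3 lists "Non-EMA Estimand with an additional covariate, CAP score, included in the analysis model", with a matching entry for the EMA estimand, both under a lead-in that makes them optional. Section 7.6 uses a closely related age-by-CAG term in a score "defined as prognostic index for HD". Section 9.1.2 names CAP among covariates that might affect the efficacy endpoints.

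**Availability.** At least 36 CAG repeats is an entry criterion (Protocol 5.1). CAG is reported by the participant or measured by a laboratory (SAP 6.2), and age is on the eCRF (SAP 5.5.2). A missing baseline covariate is mean-imputed (SAP 5.8.1.1), so adjusting for CAP need not lose anyone.

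**Imputation.** For the EMA analysis, Protocol 9.4.2 imputes visit by visit. Each visit has its own regression containing Baseline TFC; none contains CAP.

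**Sample size (SAP 3.3).** "A total sample size of 372 participants will provide 94% power to detect a between-group difference of 0.7 points", "with an SD of 1.9 points", "using a two-tailed t-test at a significance level of 0.05". For the EMA case: "A difference of 0.565 points with SD of 1.9 with a sample size of 480 participants would provide 90% power".

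**The concern.** Adjusting a randomized comparison for a baseline variable that predicts outcome reduces residual variance and leaves the target treatment difference unchanged. The SAP treats CAP as a plausible predictor in several places, yet keeps it out of the one model where added precision would matter most.

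The Baseline TFC slope raises a similar question. Categorical week and treatment-by-week capture the mean course of change, but they do not let the relation between Baseline TFC and change differ by visit. Protocol 8.1.1 describes a rate of decline that depends on TFC level: 0.8 to 1.2 units a year at TFC 7–13 against 0.2 to 0.3 at TFC 3–6. That compares stages and does not give slopes within 7–13. Still, where rate depends on level, the effect of Baseline on change would grow with time. The EMA analysis also mixes two assumptions: the imputation regressions free the slope by visit, and the MMRM fitted to the imputed data then constrains it.

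The primary test gates nine ranked secondary endpoints (SAP 2 and 5.6). If it misses 0.05, every later p-value is nominal, so even small gains in precision have some value here.

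**Working it through.** **1. Reproduce the plan's figures.** Inputs from SAP 3.3: two-sided α 0.05, SD 1.9, 1:1 allocation.

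- SE = SD × √(2/n per arm). With 186 per arm, SE = 1.9 × √(2/186) = 0.197. The noncentrality is 0.7/0.197 = 3.55, and noncentral-t power is 94.3% (stated 94%).
- EMA case: 0.7 × 0.775 + 0.1 × 0.225 = 0.565. With 240 per arm, SE = 1.9 × √(2/240) = 0.173, and power is 90.2% (stated 90%).
- Drop-out: 372/(1 − 0.225) = 480.

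All reproduce. The calculation is an unadjusted t-test, so the stated power counts on no gain from covariates.

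**2. Add CAP.** Let R² be CAP's partial R² for Week 65 change, given the covariates already in the model. The residual SD is 1.9 × √(1 − R²), so the SE falls by 1 − √(1 − R²). The equivalent extra evaluable participants are 372/(1 − R²) − 372. **R² is an assumption; the documents give no value.**

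| Assumed R² | Residual SD | SE reduction | Power, N=372, 0.7 | Power, N=480, 0.565 | Extra evaluable equivalent |
|---|---|---|---|---|---|
| 0 | 1.900 | – | 94.3% | 90.2% | – |
| 1% | 1.890 | 0.5% | 94.5% | 90.4% | 4 |
| 2% | 1.881 | 1.0% | 94.7% | 90.7% | 8 |
| 5% | 1.852 | 2.5% | 95.3% | 91.6% | 20 |
| 10% | 1.802 | 5.1% | 96.2% | 92.9% | 41 |

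The last column uses 372 because the 94% figure does. On the 480 randomized, the equivalents at 2%, 5% and 10% would be 10, 25 and 53; the two bases should not be mixed.

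**3. CAP as main effect or by week.** The table assumes the model captures all of CAP's Week 65 effect. Suppose instead that CAP's effect grows in proportion to time (assumed visit SDs 1.2, 1.5, 1.7, 1.9; autoregressive correlation 0.5 to 0.85; R² 2% to 10%). A single CAP slope then recovers roughly 65% to 85% of the SE reduction, and CAP × week recovers all of it.

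**4. Add Baseline TFC × week.** The documents give no Baseline slopes by visit, so this was simulated: 372 participants, four visits, complete data, unstructured covariance, 300 runs per scenario. Assumed: Baseline SD 1.5, visit SDs as above, autoregressive correlation 0.7.

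| Assumed Baseline slopes, Weeks 26, 39, 52, 65 | Week 65 SE, with / without the term |
|---|---|
| 0, 0, 0, 0 | 1.000 |
| −0.05, −0.08, −0.12, −0.15 | 0.998 |
| −0.05, −0.12, −0.20, −0.30 | 0.988 |
| 0, −0.15, −0.30, −0.45 | 0.962 |

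The mean treatment estimate was essentially the same with and without the term (for example 0.707 and 0.708 in the last scenario). The gain is about 1% or less unless the slope changes steeply between visits.

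**The case against.** The strongest reply is that nothing here is a defect. The planned model adjusts for Baseline TFC, both stratification factors and region. Under randomization it targets the same difference with or without the extra terms, and the stated power relies on neither. That stands. A reader might infer that the primary analysis is biased or underpowered; the documents do not support it.

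A reader might also infer that precision is certainly lost and could be recovered for nothing. Neither part is shown. Use of CAP as a subgroup factor concerns effect modification, not prognosis. The index in SAP 7.6 combines TMS, SDMT and age × (CAG − 34), which is not the CAP of 7.3.2. CAP could add little once Baseline TFC and HD stage are in the model.

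Other points also carry weight:

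- **Power may already exceed the plan.** The SAP reports 499 randomized and a low discontinuation rate. With 10% drop-out (an assumption), 499 × 0.9 = 449 evaluable gives 97.4% power at 0.7 and SD 1.9; CAP at R² 5% adds about 0.6 points.
- **The missing-data benefit is small.** In-clinic TFC completion was 98.9% as of October 2022 (SAP 3.6.3.1), so a more plausible missing-at-random assumption has little to act on.
- **CAG quality is mixed.** Some values are participant-reported, and the SAP's change table regards laboratory values as more reliable. This could weaken CAP as a covariate but cannot bias the comparison.
- **The change is late.** The primary analyses were set after regulatory feedback, and Protocol 9 says that major differences from the SAP on the primary analysis prompt consideration of an amendment.

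These points limit the size and urgency of the point. They do not explain why CAP-adjusted analyses of both estimands remain optional, or why the imputation frees a slope that the analysis model constrains.

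**Conclusion.** The point holds as an inexpensive, optional improvement in efficiency. The primary MMRM is valid and its power figures reproduce. It *may* give up modest precision: 0.5% to 5.1% of the Week 65 SE from omitting CAP, if CAP's partial R² lies between 1% and 10%, and 0% to about 4% from the single Baseline TFC slope, under the slopes tried. For CAP that is 0.2 to 1.9 points of power at N=372 and 0.3 to 2.7 points in the EMA case. Both ranges rest on assumptions that the documents can neither confirm nor rule out, and the true gain could be close to nil. The firmest findings need no assumption: the two CAP-adjusted analyses are only optional, and the EMA imputation and analysis models treat the Baseline slope differently.

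**What to change.** Before unblinding:

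1. Add CAP score (preferably CAP × week) and Baseline UHDRS-TFC × week to the primary MMRM, with the same wording in SAP 7.2 and Protocol 9.4.2.
2. Add CAP to the imputation models in SAP 5.8.1.2 and Protocol 9.4.2, so that they match the analysis model.
3. Keep the present model as a sensitivity analysis that will definitely be run.

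If the sponsor prefers to leave the primary model alone, the minimum is to change *may* to *will* for the two CAP-adjusted analyses in SAP 7.3.3.

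**Cost.** Over four visits, Baseline × week takes three further degrees of freedom; CAP takes one, or four if by week. That is negligible with several hundred participants. The real cost is aligned Protocol and SAP text, revised imputation programs, and notifying regulators of a changed primary model. The minimum version needs only a wording change in SAP 7.3.3.
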